#### **3.2 Protocol Deviations**

Both major and critical protocol deviations, as defined by the Protocol Deviation (PD Plan, will be summarized. Per the PD Plan, a major deviation is one that resulted or had the potential to result in non-life-threatening harm to an individual participant or had the potential to affect the safety and well-being of trial subjects or the reliability of clinical trial data. The event did not pose a significant risk to the overall project, overall subject safety, or overall data quality/ integrity. A critical deviation is a significant departure from GCP resulting in a life-threatening risk to an individual subject, or where the safety or well-being of trial subjects was or had significant potential to be jeopardized or caused a significant portion of the clinical trial data to be potentially unreliable.

Of particular note are deviations related to the protocol-mandated oral glucocorticoid taper that begins on RCP Day 1 and lasts for 8 weeks. Each incident of a variation from the protocol-specified taper regimen will be recorded as a minor PD. These deviations will be analyzed per subject, and a major PD will be recorded if the departure from the prescribed regimen is substantial, defined as either of the following:

- The total dose for steroid tapering is > 20% more or > 20% less than the protocolspecified total dose of 700 mg of prednisone or equivalent (i.e., > 840 mg or < 560 mg)
- The total duration for steroid tapering is > 20% longer or > 20% shorter than the protocol-specified duration of 56 days (i.e., > 67 days or < 45 days)

The list of the protocol deviations and the corresponding classification may be reviewed, finalized and documented prior to unblinding the study.

#### 3.3 Analysis Sets

#### 3.3.1 Full Analysis Set (FAS)

The Full Analysis Set includes all subjects who receive any dose of IP during the RCP. Subjects will be analyzed according to the treatment assignment. The efficacy analyses will be based on the Full Analysis Set.

#### 3.3.2 Safety Analysis Set (Randomized-controlled Period)

The Safety Analysis Set includes all subjects who received any dose of IP during the RCP, and will be used for safety, , and ADA analysesFor the analyses in the RCP, subjects will be analyzed according to the treatment that they actually received. Specifically, subjects randomized to the inebilizumab group who received all placebo dose will be included in the placebo group; conversely, subjects randomized to the placebo group who received at least one dose of inebilizumab will be included in the inebilizumab group.

#### 3.3.3 Open-label Analysis Set

The Open-Label Analysis Set includes all subjects who received any dose of inebilizumab during the OLP.

#### 3.3.4 Any Inebilizumab Analysis Set

The Any Inebilizumab Analysis Set includes all subjects who received any dose of inebilizumab during the study. Analyses with this analysis set will be based on the data collected on or after subjects receive the first administration of inebilizumab.

#### 3.3.6 Safety Follow up Analysis Set

The Safety follow up Analysis Set includes all subjects who are eligible for the SFP.

#### 3.4 Study Subjects

#### 3.4.1 Subject Disposition

Subject disposition will be summarized using all the screened subjects. The total number of subjects will be summarized for those who are screened; who are screen failed and who are randomized. And the numbers and the percentages of the subjects will be summarized for following groups.

- Subjects who are randomized
- Subjects who discontinued treatment during the RCP
- Subjects who early discontinued from the RCP
- Subjects who completed RCP
- Subjects who entered OLP
- Subjects who discontinued treatment during the OLP
- Subjects who early discontinued from the OLP
- Subjects who entered SFP
- Subject who discontinued from the SFP

A Kaplan-Meier (KM) curve of the time to RCP discontinuation by treatment arm will be produced.

#### 3.4.2 Demographics, Baseline Characteristics, and Medical History

The following demographics, baseline characteristics, and medical history will be summarized for Full Analysis Set by treatment group.

#### 3.4.2.1 Demographics

- Age (years)
- Age category (< 65,  $\geq 65$  years)
- Sex (Male and Female)
- Race (American Indian or Alaskan Native, Asian, Black or African American, Native Hawaiian or Other Pacific Islander, White, Other)
- Ethnicity (Hispanicor Latino vs NotHispanic or Latino).
- Region (US vs Non-US; EU vs non-EU; Asia vs non-Asia; Japan vs non-Japan)
- Height (cm)
- Weight (kg)
- BMI  $(kg/m^2)$
- BMI category (< 18.5,  $\geq 18.5 \langle 25, \geq 25 \langle 30, \geq 30 \rangle$ )

#### 3.4.2.2 Baseline Characteristics

Table 3 provides the list of baseline characteristics to be summarized along with type of summary.

#### **Table 3 Baseline Characteristics**

- IgG4-RD manifestation (newly diagnosed vs recurrent) n (%)
- Disease duration (years) defined as the years between date of diagnosis and date of 1st administration of IP, calculated as (date of 1st IP administration date of diagnosis + 1)/365.25 descriptive statistics
- Number of organs ever affected by IgG4-RD (1, 2, 3, etc.)
- List of organs previously affected (meninges, pituitary gland, etc. "other" counts as 1) n (%)
- Highest known IgG4 serum level descriptive statistics
- Category of highest IgG4 serum level (< median vs  $\geq$  median) n (%)
- IgG4-RD RI descriptive statistics
- Prior non-glucocorticoid therapy for IgG4-RD (yes / no) n (%)

#### 3.4.2.3 Medical History

Medical history and procedure history for IgG4-RD will be summarized by MedDRA system organ class (SOC) and preferred term (PT).

#### 3.4.3 Study Drug Exposure

Study drug exposure, which includes number of doses, dose amount and dose amount adjusted for weight (mg/kg) of the study drug, and durations of the study drug exposure, will be summarized for RCP, OLP, and Any Inebilizumab exposure by treatment group. In addition, treatment compliance will also be summarized for RCP.

The amount of study drug exposure: If entire dose was administered, the dose amount (mg) at a specific visit will be either 0 or 300 mg depending on what treatment the subject had received; if a subject received partial dose at a dosing visit, then the amount of study

drug at that dosing visit will be estimated based on the actual volume administered. For example, if a subject receives 175 mL (instead of the full 250 mL), the dose amount (mg) will be estimated as =  $300 \text{ mg} \times 175 \text{ mL} / 250 \text{ mL} = 210 \text{ mg}$  provided the subject received inebilizumab.

Treatment compliance for an individual subject = [Total number of doses received]/ [Total number of doses planned per protocol]  $\times 100\%$ .

The definition of duration of study drug exposure and person-years of exposure is outlined in Table 4.

RCP	OLP	Combined RCP and OLP (Any Inebilizumab Exposure)	
	Duration of study drug exposure		
Last RCP dose date $-1^{st}$ RCP dose date $+90^{a}$	Last OLP dose date $-1^{st}$ OLP dose date $+90^{a}$	Last inebilizumab dose date – 1 st inebilizumab dose date + 90 a	
Person-year definition for individual subject b			
$\begin{array}{c c} (\text{Date of last RCP day} - 1^{\text{st}} \text{ RCP dose} \\ \text{date} + 1)/365.25 \end{array} \\ \begin{array}{c c} (\text{Date of last OLP day} - 1^{\text{st}} \text{ OLP} \\ \text{dose date} + 1)/365.25 \end{array} \\ \begin{array}{c c} (\text{Date of last study day in RCP or} \\ \text{OLP} - 1^{\text{st}} \text{ inebilizumab dose date} + 1)/365.25 \end{array} \\ \end{array}$			
a Based on 5 half-lives (18 days) determined from previous late-stage clinical trials			
b Total person-years will be calculated as the sum of the person-years for individual subject			

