7 STUDY INTERVENTIONS

7.1 Description of Investigational Products

Table 7 provides a description of the IPs to be used in the study.

Investigational Product	Concentration and Formulation as Supplied	Route Dose	RCP Dosing Regimen	Manufacturer
Inebilizumab (100 mg per vial, nominal)	Inebilizumab for IV administration is supplied as a sterile liquid filled at a nominal volume of 10 mL in 10R vials. Each vial contains inebilizumab formulated at 10 mg/mL, in 20 mM histidine/histidine hydrochloride, 70 mM NaCl, 106 mM (4% [w/v]) trehalose dihydrate, and 0.01% (w/v) polysorbate 80, pH 6.0	IV 300 mg	Day 1, Day 15, and Week 26	AstraZeneca Nijmegen, B.V. (formerly MedImmune Pharma, BV)
Placebo	Placebo for IV administration is supplied in 10R vials filled with 10 mL (nominal) solution containing 10 mM histidine/histidine hydrochloride, 75 mM NaCl, 106 mM (4% [w/v]) trehalose dihydrate, and 0.02% (w/v) polysorbate 80, pH 6.0	IV	Day 1, Day 15, and Week 26	AstraZeneca Nijmegen, B.V. (formerly MedImmune Pharma, BV)

Table 7Description of Investigational Products and RCP Dosing

Table 7Description of Investigational Products and RCP Dosing

Investigational Product	Concentration and Formulation as Supplied	Route Dose	RCP Dosing Regimen	Manufacturer
				Berkshire Sterile Manufacturing, Inc.

IV = intravenous; NaCl = sodium chloride; RCP = randomized-controlled period; w/v = weight/volume.

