7.1.1.3 Investigational Product Dose Preparation

Inebilizumab for IV administration and placebo for IV administration are supplied as a sterile liquid in a 10R glass vial at a nominal fill volume of 10 mL with 20-mm stopper and flip-off cap overseal.

No incompatibility has been observed between inebilizumab or placebo and IV infusion bags made of polyolefin or polyvinyl chloride. Inebilizumab and placebo do not contain preservatives and any unused portions must be discarded. Preparation of IP and IV bags is to be performed aseptically.

To prepare each inebilizumab or placebo dose, 3 vials of IP, one 250 mL IV bag containing 0.9% (weight/volume) saline, and one IV infusion pump are required. Each vial should be used only one time to prepare a single dose. With approval of the Sponsor (and using additional

administration instructions), 100 mL or 500 mL saline bags may be used if 250 mL bags are not available or not appropriate.

The dose preparation steps are as follows:

- The tab portion of the vial cap should be removed and the rubber stopper cleaned with 70% ethyl alcohol or equivalent.
- For each dose, 30 mL of blinded IP will be obtained from 3 vials by withdrawing 10 mL from each vial. Use a new needle for each withdrawal.
- Add 30 mL of blinded IP to the saline bag using aseptic technique.
- Gently mix the contents of the IV bag by inversion. Do not shake the solution. The saline bag should then be inspected to ensure the solution is clear.

Total in-use storage time from needle puncture of the IP vials to start of administration should not exceed 4 hours at room temperature or 24 hours at 2°C to 8°C (36°F to 46°F). Although prepared IP is stable for 24 hours at 2°C to 8°C (36°F to 46°F), the dose of IP must be mixed on the day of administration.

The prepared infusion solution should be at room temperature prior to the start of the IV infusion.

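### The SAP's partial-dose example takes 250 mL as the full infusion volume, but the protocol's preparation steps imply 280 mL, so estimated partial doses from a standard bag come out 12% too high

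*SAP*

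**What the plan says.** SAP 3.4.3 (Study Drug Exposure) plans summaries of the number of doses, dose amount in mg, dose amount per kg of body weight, and duration of exposure, for the randomized period, the open-label period and any inebilizumab exposure. For a complete infusion, "the dose amount (mg) at a specific visit will be either 0 or 300 mg depending on what treatment the subject had received". For an incomplete one, the amount "will be estimated based on the actual volume administered". That rule names no denominator. The illustration that follows supplies one: "if a subject receives 175 mL (instead of the full 250 mL", computed as 300 mg × 175 / 250 = 210 mg.

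The protocol describes the infusion as follows.

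- Table 7 (Section 7.1): "Each vial contains inebilizumab formulated at 10 mg/mL".
- Section 7.1.1.3, starting material: "one 250 mL IV bag containing 0.9% (weight/volume) saline".
- Section 7.1.1.3, product: "30 mL of blinded IP will be obtained from 3 vials by withdrawing 10 mL from each vial", and then "Add 30 mL of blinded IP to the saline bag using aseptic technique". No step takes saline out of the bag first.
- Section 7.1.1.3, exception, with the sponsor's agreement and further instructions: "100 mL or 500 mL saline bags may be used if 250 mL bags are not available or not appropriate".
- Section 7.1.1.4: unless an infusion reaction ends the infusion, the full content of the bag is to be given and the line flushed.

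**The concern.** A proportional estimate of a partial dose is only as good as the volume taken as 100%. The SAP takes the labelled size of the saline bag. The protocol's steps put the 300 mg into that saline plus 30 mL of product. If so, each millilitre infused carries less drug than the SAP assumes, and every partial dose is estimated too high by the same factor.

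Little is at stake, but the effect runs in one direction. It touches only subjects whose inebilizumab infusion was incomplete, and for them it inflates the mg and mg/kg figures. Because the SAP sets no upper limit, an infusion stopped near its end could also appear in a listing with more than the planned 300 mg.

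**Working it through.** **Inputs**

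- Drug per dose: 10 mg/mL × 30 mL = 300 mg (Protocol Table 7 and Section 7.1.1.3).
- Saline in the standard bag: 250 mL nominal (Section 7.1.1.3).
- Product added: 3 × 10 mL = 30 mL, with no saline withdrawn (Section 7.1.1.3).
- Implied nominal prepared volume: 250 + 30 = 280 mL. Neither document states this total.

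**The SAP's figure.** 300 × 175 / 250 = 210 mg. It reproduces exactly.

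**The same case on the protocol's steps.** 300 × 175 / 280 = 187.5 mg.

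**Size of the discrepancy.** The ratio of the two estimates is 280 / 250 = 1.12 whatever the volume infused, so the overstatement is a constant 12%. Body weight cancels, so mg/kg is overstated by the same 12%.

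| Volume infused (standard bag) | Dividing by 250 | Dividing by 280 |
|---|---|---|
| 100 mL | 120.0 mg | 107.1 mg |
| 175 mL | 210.0 mg | 187.5 mg |
| 250 mL | 300.0 mg | 267.9 mg |
| 260 mL | 312.0 mg | 278.6 mg |
| 279 mL | 334.8 mg | 298.9 mg |

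**When the estimate passes 300 mg.** This needs a partial volume above 250 mL and below 280 mL. The ceiling is just under 300 × 280 / 250 = 336 mg.

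**Check against the infusion rates in Protocol Table 8.** The first 30 minutes deliver 42 × 0.5 = 21 mL and the next 30 minutes deliver 125 × 0.5 = 62.5 mL, together 83.5 mL. At 333 mL/hour, the remaining 166.5 mL of a 250 mL volume takes 30 minutes, so the infusion ends at 90.0 minutes. The remaining 196.5 mL of a 280 mL volume takes 35.4 minutes, so it ends at 95.4 minutes. The rates fit 250 mL neatly, but the last row runs to the end of the infusion, so they accommodate 280 mL as well.

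**Other bag sizes.** The same steps imply 100 + 30 = 130 mL and 500 + 30 = 530 mL. The SAP gives no denominator for either. If the labelled bag size were used by analogy with the example, the overstatement would be 130 / 100 − 1 = 30% for the 100 mL bag and 530 / 500 − 1 = 6% for the 500 mL bag.

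**The case against.** The best defence is that the SAP's rule rests on the volume administered and that 250 mL appears only in an illustration. Table 8 delivers exactly 250 mL in 90 minutes, which suggests that the protocol itself may work with a nominal 250 mL. No final volume is stated anywhere, and actual bag fill is unknown.

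Part of this stands: 280 mL is inferred from the written steps. But the illustration is the only formula the SAP offers a programmer, and it calls 250 mL the full volume. Table 8 names the bag size and leaves its last step open-ended, so it does not settle the final volume. Overfill beyond the nominal 250 mL would widen the gap. If 250 mL really is the intended final volume, the preparation steps lack a withdrawal step and the two documents still disagree.

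Four stronger readings are tempting and are not supported.

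- A reader might divide by 250 for the other bags. A half-infused 500 mL bag (265 of 530 mL) would then give 318 mg against 150 mg, and a half-infused 100 mL bag (65 of 130 mL) would give 78 mg against 150 mg. The SAP does not tell anyone to do this. For those bags the fault is a missing denominator, and the additional instructions that the protocol mentions are not part of these documents.
- A reader might infer that estimates above the full dose would be common. With the standard bag they need an infusion stopped within the last 30 mL, about 5.4 minutes at the Table 8 rate.
- A reader might infer that recorded doses are wrong. The SAP's calculation is an analysis estimate and leaves the site's dosing record unchanged.
- A reader might infer that most affected subjects had infusion reactions. A reaction that stops the infusion is the one exception Section 7.1.1.4 names, but neither document says how often infusions are cut short or why.

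**Conclusion.** The SAP's worked example is inconsistent with the protocol's preparation steps. Taking those steps as written, with nominal volumes and no saline removed, the example should read 187.5 mg rather than 210 mg, and each estimated partial dose from a standard bag is 12% too high. If the final volume were in fact brought to 250 mL, the error would be zero and the protocol steps would be the part needing correction. The plausible range at nominal fill is therefore 0% to 12%, and the written text points to 12%.

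The consequence is minor. Complete infusions are assigned 300 mg directly, and placebo infusions are 0 mg either way. Compliance counts doses, while exposure duration and person-years use dates. No efficacy analysis, adverse event rate or test in the multiplicity scheme uses the estimate. Only the descriptive mg and mg/kg summaries for incomplete inebilizumab infusions change. It is worth correcting because the text is wrong as it stands and the repair takes one line.

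**What to change.** In SAP 3.4.3, define the estimated dose for an incomplete inebilizumab infusion as 300 mg × volume infused / total prepared volume of the bag used, capped at 300 mg. Take the total prepared volume as recorded or, failing that, as the nominal saline volume plus 30 mL: 130, 280 or 530 mL for the 100, 250 and 500 mL bags. Replace the worked example with 300 × 175 / 280 = 187.5 mg.

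Reconcile SAP 3.4.3 with Protocol 7.1.1.3 and Table 8 by having the sponsor state the intended final volume after dilution. If that volume is not the saline plus 30 mL, the denominators and the example follow the stated volume.

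The cost is one formula and one example in the SAP. The only practical demand is that bag size or prepared volume be available in the dosing record. If it is not collected, it would have to be retrieved, but only for incomplete infusions.

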#### Table 4 Investigational Product Exposure Summary

#### 3.4.4 **Prior and Concomitant Medications**

Number (%) of subjects who received prior medications and concomitant medications will be summarized by WHO Drug dictionary. Rescue medications will be summarized separately from other concomitant medications. At each level of summarization, a subject is counted once if the subject reported one or more medications at that level. The prior and concomitant medications are defined as below:

- Prior medications are defined as medications with a stop date occurring before the first RCP dose date.
- Concomitant medications for RCP are defined as:
  - 1) Medications started on or after first RCP dose date, and on or before the end of RCP, or
  - 2) Medications stopped on or after first RCP dose date, and on or before the end of RCP, or
  - 3) Medications started before the first RCP dose date, and ongoing at the end of RCP.
- Concomitant medications for OLP are defined as:
  - 1) Medications started on or after the first OLP dose date, and on or before the end of OLP, or
  - 2) Medications stopped on or after the first OLP dose date, and on or before the end of the OLP, or

3) Medications started before the first OLP dose date, and ongoing at the end of the OLP.

Descriptive summaries and by-subject listings of corticosteroid use for protocol-specified taper, for flare treatment, and for other reasons will be provided.

#### 3.5 Efficacy Analyses

#### 3.5.1 Primary Efficacy Endpoint and Analysis

#### 3.5.1.1 Primary Efficacy Endpoint and Primary Analysis

The Primary efficacy endpoint is time to disease flare, defined as the time in days from Day 1 (dosing) to the date of the first treated and AC-determined IgG4-RD flare within the 52-week RCP. The date of disease flare is defined as the date of initiation of any flare treatment (new or increased GC treatment, other immunotherapy, or interventional procedure) deemed necessary by the Investigator for the flare.

The estimand with a treatment policy strategy is defined by the following:

- Target population: Subjects in the FAS
- Variable: Time in days from Day 1 (dosing) to the date of the first treated and ACdetermined IgG4-RD flare within the 52-week RCP. Date of flare onset is defined as date of onset of treatment (medication or procedure).
- Intercurrent event: All data captured during the 52-week RCP will be used for analysis. Subjects who do not complete the RCP and who have not had a treated and AC-determined flare during the RCP will be censored at the time of discontinuation.
- Population-level summary: Hazard ratio (HR) between inebilizumab versus placebo and its associated 95% CI.

To assess the robustness towards violations of the assumption of non-informative censoring of subjects who do not complete the RCP, the following sensitivity analysis will be performed:

- Target population: Subjects in the FAS
- Variable: Time in days from Day 1 (dosing) to the date of the first treated and ACdetermined IgG4-RD flare within the 52-week RCP. Date of flare onset is defined as date of onset of treatment (medication or procedure).
- Intercurrent event: All data captured during the 52-week RCP will be used for analysis. Subjects who do not complete the RCP due to IgG4-RD related death or due to subject perception of lack of efficacy and who have not had a treated and AC-determined flare will be considered as having a flare with onset at the time of discontinuation / withdrawal from the RCP. Subjects who do not complete the RCP due to other reasons and who have not had a treated and AC-determined flare will be censored at the time of discontinuation / withdrawal from the RCP.
- Population-level summary: HR between inebilizumab versus placebo and its associated 95% CI.

The hazard rate in the inebilizumab group will be compared to that in the placebo group using the Cox proportional hazards model with the treatment indicator (inebilizumab or placebo) and the stratification factor as the explanatory variables. The HR of inebilizumab versus

placebo will be estimated together with its associated 95% CI. The two-sided p-value for the treatment effect will be determined using Cox proportional regression model. SAS PROC PHREG will be used for fitting this model.

